5.10. Pharmacokinetic Analyses

For eteplirsen-treated patients, individual plasma levels of eteplirsen will be listed with the corresponding time related to eteplirsen administration and summary statistics will be generated by per-protocol time of collection.

Pharmacokinetic parameters for eteplirsen will be calculated using non-compartmental analysis. Actual sampling times will be used in all final PK analyses; per protocol times will be used to calculate mean plasma concentrations for graphical displays. The PK parameters that will be determined include: C_{max}, t_{max}, AUC, V_{ss}, t_{1/2}, CL, MRT and CLR.

Plasma concentration-time data of eteplirsen will be used to perform a future population PK analysis using nonlinear mixed-effects modeling. Data may be combined with those of completed studies to support a relevant structural model.

The details of PK analyses will be described in a separate PK SAP.

6. CHANGES IN PLANNED ANALYSES

6.1. Changes from Clinical Protocol-Planned Analyses

Compared to protocol specified analyses, the changes are made as follows:

- CCI [REDACTED]
- CCI [REDACTED]
- The observed values and changes from baseline for clinical laboratory assessments, vital signs and ECG will only be summarized for baseline, the last visit (final observation) and the highest/lowest values. All clinical laboratory assessments, vital signs and ECG results by visit will be in data listing.
- The untreated patient group is intended to evaluate the natural history of the DMD disease for patients who are not amenable to exon 51 skipping and is not considered eligible as a current control group for eteplirsen treated patients due to the following: 1) only 7 patients not amenable to exon 51 skipping were enrolled as supposed to planned 20 patients in untreated group, 2) untreated patients have much less assessment frequency of adverse events during study, 3) most untreated patients have dropped out the study earlier. Thus, no direct comparison is made between eteplirsen treated patients and untreated patients. No hypothesis test, no p-value and no inferential statistics will be made for comparison of eteplirsen treated patients and untreated patients.
- Due to complexity of identifying an external control dataset, the statistical methods for the identification and use of the external control dataset will not be described in this SAP. No analysis of eteplirsen-treated patients as compared to an external control will be performed.
- If an external control is identified in the future, the analysis results may not be included in the CSR, and may be reported in a standalone report.
- CCI [REDACTED].
- No other changes are planned or made.

6.2. Changes from Previous Statistical Analysis Plans

Compared to previous Muscle Biopsy SAP, the changes are made as follows:

- A revision of the muscle biopsy SAP is made to integrate the analyses of muscle biopsy endpoints into this SAP as final analyses of all efficacy endpoints for supporting CSR.
- The previously planned interim analysis of muscle biopsy-based endpoints was not performed.
- Due to evaluation of analytical method for exon 51 skipping in skeletal muscles as determined by CCI [REDACTED], the statistical method of analyzing exon 51 skipping is revised to be the same as the methods for other biopsy based endpoints.

7. APPENDIX 1: ABNORMALITIES OF INTEREST

Appendix Table 1. Chemistry Laboratory Abnormalities of Interest

Test	Unit	Predefined Change		Markedly Abnormal Criteria
		Decrease	Increase	
BUN	mmol/L	NA	NA	Value >1.5× Baseline and >ULN
Creatinine	μmol/L	NA	35	Value > ULN
Sodium	mmol/L	8	8	NA
Potassium	mmol/L	1.1	1.0	Value >5.5 mmol/L or <3 mmol/L
Chloride	mmol/L	9	8	NA
Uric acid	μmol/L	NA	NA	>1×ULN
Calcium	mmol/L	0.30	0.30	NA
AST (SGOT)	U/L	NA	NA	Value ≥2× Baseline Value and >ULN
ALT (SGPT)	U/L	NA	NA	Value ≥2× Baseline Value and >ULN
Gamma glutamyltransferase	U/L	NA	NA	Value >3× Baseline Value and > ULN
Alkaline phosphatase	U/L	NA	NA	Value >1.5 × ULN
Albumin	g/L	10	10	< LLN or >ULN
Total bilirubin	μmol/L	NA	10	Value >1.5× ULN
Lactate dehydrogenase	U/L	NA	NA	Value ≥2× Baseline Value
Creatine phosphokinase	U/L	NA	NA	Value ≥2× Baseline Value
Cystatin C	mg/L	NA	NA	>ULN

ALT = alanine aminotransferase; AST = aspartate aminotransferase; BUN = blood urea nitrogen; LLN = lower limit of normal; NA = Not Applicable; ULN = upper limit of normal

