11.3.3. Clinical Laboratory Evaluations

The following routine clinical laboratory tests will be collected for eteplirsen-treated patients at the time points specified in [Section 2](#) and analyzed by an accredited central laboratory selected by the Sponsor and prepared according to the Laboratory Manual provided for the study:

Chemistry:	Sodium, chloride, potassium, calcium, glucose, creatinine, blood urea nitrogen (BUN), albumin, uric acid, total bilirubin, alkaline phosphatase, amylase, alanine aminotransferase (ALT), aspartate aminotransferase (AST), gamma-glutamyl transferase (GGT), lactate dehydrogenase (LDH), C-reactive protein (CRP), creatine kinase (CK), and serum cystatin C
Hematology:	Red blood cells (RBCs), total white blood cells (WBCs), hemoglobin, hematocrit, neutrophils, lymphocytes, monocytes, eosinophils, basophils, platelets, and abnormal cells
Coagulation Screen:	Prothrombin time, International Normalized Ratio (INR), and activated partial thromboplastin time (aPTT)
Urinalysis:	pH, specific gravity, protein, glucose, ketones, cytology, hemoglobin, and kidney injury molecule-1 (KIM-1)

Any value outside of the current reference ranges for the laboratory performing the test will be flagged on the laboratory results. The Investigator will determine whether abnormal assessment results are clinically significant (CS) or not clinically significant (NCS). Clinical significance is defined as any variation in assessment results that has medical relevance resulting in an alteration

in medical care. If clinically significant deterioration from baseline levels is noted, the Investigator will continue to monitor the patient with additional assessments until:

- Values have reached normal range and/or baseline levels; or
- In the judgment of the Investigator together with the Sponsor's Medical Monitor, abnormal values assessed to be not related to the administration of investigational product or other protocol-specific procedures, and additional assessments are not medically indicated.

Patients in the untreated control group will also undergo laboratory testing at the time points specified in [Section 3](#).

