5.8.2 Adverse Events of Special Interest

Summaries of TEAEs of special interest will be summarized by SOC and PT. All standard MedDRA queries (SMQs based on MedDRA version 17.1) listed below will include broad and narrow terms. The AEs of special interest (AESI) are:

- Hypersensitivity (hypersensitivity SMQ)
- Renal toxicity (acute renal failure SMQ)
- Infusion-related reaction (IRR) (AEs occurring within 24 hours of the start of any infusion [including events that occurred on the same date as an infusion where infusion start time or AE onset time was not reported])

For all IRRs as defined above, adjudicated IRRs will be identified by a pharmacovigilance physician. All IRRs as defined above that are considered as related to study drug by investigators will be counted in the list of adjudicated IRRs. In addition, all

IRRs as defined above that meet the following criteria will be excluded from the list of adjudicated IRRs:

- AE was an infusion site, application site, or other local AE not associated with IRR
- AE had a clear alternate etiology that could be ascertained based on the reported event (eg, reaction to plaster, assessed as related to procedure or underlying disease by investigator)
- AE not associated with an IRR due to the nature of the event or biologically implausible (eg, fibula fracture, chalazion)

A summary table will be generated and include the following:

- Number of patients with adjudicated IRRs
- Number of adjudicated IRRs
- Number of adjudicated IRRs with event start time reported
- Number of events on any day for adjudicated IRRs

A corresponding listing will be generated for each table. Additionally, a table and listing corresponding to the AESIs that were related to study drug or moderate or severe will be produced.

An overall summary of AESI events will include the total number of events, number of serious events, number of related events, number of not related events, number of mild events, number of moderate events, number of severe events, and number of events occurring on the same day as an infusion.

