5.8.4 Clinical Laboratory Evaluation

Clinical chemistry, hematology, coagulation, and urinalysis results will descriptively be summarized by treatment group and by selected time point. Baseline value, highest/lowest postbaseline value, and final observation and the corresponding change from Baseline will be summarized for treated patients and untreated patients. Frequency tables of patients with potentially clinically significant laboratory parameter values at any time point will be generated. The total number of potentially clinically significant values will also be summarized. Potentially clinically significant values can be found in Appendix 1 tables 1-3.

A shift table will present the number and percentage of patients in each cell resulting from cross-tabulating the status (low, normal, and high) of the highest/lowest postbaseline value versus that of the baseline for each laboratory test, if applicable, by treatment group. If a specific test can have both a significant low and high, then a shift table will be generated for each direction. The percentage will be based on the total number of patients in the Safety Set.

All patient-level clinical laboratory values will be displayed in data listings. In addition, values meeting the potentially clinically significant abnormalities criteria will be presented in data listings. Treatment-emergent abnormalities will be indicated in the listing.

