Appendix Table 3. Urinalysis Laboratory Abnormalities of Interest

Test	Markedly Abnormal Criteria
Protein in urine	> 1+
Blood in urine	Positive (+)
RBCs in urine	>0

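### SAP Appendix Table 1 has no proportional-to-baseline criterion for creatinine or cystatin C, so a boy with a low enough baseline could double his creatinine without being counted

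*SAP*

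**What the plan says.** SAP Section 5.8.4 plans a count of affected patients: "Frequency tables of patients with potentially clinically significant laboratory parameter values at any time point will be generated". For the criteria it refers to the appendix: "Potentially clinically significant values can be found in Appendix 1 tables 1-3".

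In Appendix Table 1 the creatinine row is "Creatinine μmol/L NA 35 Value > ULN". The columns are unit, predefined decrease (none), predefined increase (35) and markedly abnormal criterion (above ULN). Cystatin C is "Cystatin C mg/L NA NA >ULN", with no predefined change. BUN must meet both parts of "Value >1.5× Baseline and >ULN". AST, ALT and GGT also have a baseline multiple joined to the ULN. LDH and creatine phosphokinase have one that stands alone, at twice baseline.

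The visible text does not say whether the predefined-change and markedly-abnormal columns are alternatives or must both be met. The definition of a treatment-emergent laboratory abnormality in SAP Section 4.8 is redacted.

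The incidence of laboratory abnormalities is a safety endpoint (Protocol 8.3.1) in a study whose primary objective is safety. SAP 5.8.2 names renal toxicity as an adverse event of special interest and identifies it from adverse event terms.

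**The concern.** A fixed step of 35 μmol/L is a change from baseline, but its meaning depends on where the boy starts. It is a 50% rise from 70 μmol/L and a doubling from 35. The ULN criterion ignores the starting value altogether. A boy who starts well inside the reference range therefore has room for a large proportional rise before either limit is reached.

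The other range-based outputs have the same limitation. Cystatin C and BUN cannot be flagged until the value passes the ULN. The laboratory's own flag (Protocol 11.3.3) uses the reference range. The shift table in SAP 5.8.4 would show a within-range doubling as normal to normal.

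With about 20 treated boys, one or two individual signals matter. SAP 6.1 restricts the laboratory summaries to baseline, last, and highest or lowest values, and rules out comparison with the untreated group. Change within the patient is then the natural reference, and the frequency table is where a reader would look for the number of boys affected.

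**Working it through.** **Inputs from the documents.** Creatinine: predefined increase 35 μmol/L; markedly abnormal above ULN (SAP Appendix Table 1). There is no derived figure in the plan to reproduce.

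**Inputs assumed.** Baseline *B* and ULN *U* are not in the documents. Illustrative values: *B* = 20, 30, 40 and *U* = 45, 55, 65 μmol/L.

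**The 35 μmol/L step alone.** Ratio to baseline when it is reached = (*B* + 35)/*B*:
- *B* = 20: 55/20 = 2.75
- *B* = 30: 65/30 = 2.17
- *B* = 40: 75/40 = 1.875
- *B* = 70: 105/70 = 1.50

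**Columns read as alternatives.** The highest unflagged value is about min(*U*, *B* + 35), so the largest unflagged ratio is min(*U*, *B* + 35)/*B*:

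| *B* | *U* = 45 | *U* = 55 | *U* = 65 |
|---|---|---|---|
| 20 | 45/20 = 2.25 | 55/20 = 2.75 | 55/20 = 2.75 |
| 30 | 45/30 = 1.50 | 55/30 = 1.83 | 65/30 = 2.17 |
| 40 | 45/40 = 1.125 | 55/40 = 1.375 | 65/40 = 1.625 |

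A doubling is possible in 4 of the 9 cells.

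**General conditions under this reading.**
- A doubling is unflagged when 2*B* ≤ *U* and the rise *B* is below 35, that is, *B* ≤ *U*/2 and *B* < 35. For *U* = 45, 55, 65 this means *B* up to 22.5, 27.5, 32.5.
- A 1.5-fold rise is unflagged when 1.5*B* ≤ *U* and the rise 0.5*B* does not exceed 35, that is, *B* ≤ 2*U*/3 and *B* ≤ 70. For *U* = 45, 55, 65 this means *B* up to 30, 36.7, 43.3.
- The table does not say whether a rise of exactly 35 counts, so the end points 35 and 70 are themselves uncertain.
- The 35 step is reached before the ULN only if *B* < *U* − 35, that is, below 10, 20 or 30. Over most of the grid the ULN is the working limit.

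**Both columns required.** The limit becomes max(*U*, *B* + 35)/*B*. At *B* = 20 this is 2.75, 2.75 and 65/20 = 3.25 for the three ULNs; at *B* = 30 it is 2.17 throughout; at *B* = 40 it is 1.875 throughout. For any *B* below 35 at least a doubling escapes, whatever the ULN.

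**The case against.** The strongest reply is that the size of the gap rests on figures that the documents do not contain. A reader might infer that creatinine could about double unflagged in these boys generally, because boys of this age with muscle disease would start low. The documents report no baseline creatinine and no reference range. Under the alternatives reading a doubling is caught at any baseline above half the ULN. This stands, and the point has to be stated conditionally.

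A reader might also infer that the plan could hide a substantial loss of renal function. That does not follow. It needs an assumed baseline, an assumed ULN and an assumed relation between creatinine and filtration. SAP 5.8.4 also summarizes the highest or lowest post-baseline value with its change from baseline, and continuous summaries include the maximum. All values are listed by patient. Urine protein, blood and red cells have their own criteria in Appendix Table 3, and KIM-1 is collected, although it has no criterion there. Protocol 11.3.3 has the investigator judge clinically significant deterioration from baseline. The renal event of special interest does not depend on Appendix Table 1. So the data are not lost. Still, none of these outputs counts boys with a proportional rise in creatinine or cystatin C.

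Finally, the comparison within the table is weaker than it looks. The multiples for BUN, AST, ALT and GGT are tied to the ULN, so the plain ULN rule for creatinine is already more sensitive than those joint rules, and copying the BUN form would add nothing. Only LDH and creatine phosphokinase offer a stand-alone precedent, and at a factor of 2. The factor 1.5 is a choice that the documents do not justify for creatinine.

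**Conclusion.** The point holds in conditional form. Creatinine and cystatin C have no proportional criterion. With the creatinine columns as alternatives, a doubling meets neither criterion when baseline is at or below half the ULN and below 35 μmol/L, and a 1.5-fold rise meets neither when baseline is at or below two-thirds of the ULN and 70 μmol/L or less. If both columns are required, the gap is wider. The algebra is certain; the number of boys affected is unknown, because baselines and ULNs are not given.

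This is a gap in tabulation for a safety endpoint. It does not show that a renal signal would be missed, since the summary of extremes and the listings remain.

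**What to change.** In Appendix Table 1, or in SAP 5.8.4 where it is cited:

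1. State whether the predefined-change and markedly-abnormal columns are alternatives or must both be met.
2. Add *Value ≥1.5× Baseline* for creatinine and for cystatin C as a separate reporting criterion, not joined to the ULN. Keep the existing criteria.
3. In the 5.8.4 frequency table, show the number of boys meeting each criterion separately.

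This changes tabulation only and leaves clinical management untouched. It needs no new data: one added criterion in two rows, and the programming for it.

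The cost is extra flags from assay variation at low values. At a baseline of 20 μmol/L the new criterion is met by a rise of 0.5 × 20 = 10 μmol/L. The Protocol Section 2 schedule gives a treated boy up to nine safety-laboratory samples after Week 1 (Weeks 4, 8, 12, 24, 36, 48, 72, 96 and End of Study) at which that could happen. The documents give no assay variation, so the number of such flags cannot be calculated; separate counts per criterion keep them visible.

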Appendix Table 2. Hematology Laboratory Abnormalities of Interest

Test	Unit	Markedly Abnormal Criteria
Hematocrit	l	<LLN
Hemoglobin	g/L (or mmol/L)	<LLN
Red blood cell count	trillion/L	<LLN
White blood cell count	10 ⁹ /L	>1.5 × ULN or <LLN
Platelet count	10 ⁹ /L	<150 or <200 with a decrease of at least 100
Basophils (abs)	10 ⁹ /L	>ULN or <LLN
Eosinophils (abs)	10 ⁹ /L	>1.5 × ULN or <LLN
Lymphocytes (abs)	10 ⁹ /L	<LLN
Monocytes (abs)	10 ⁹ /L	<LLN
Neutrophils (abs)	10 ⁹ /L	>1.5 × ULN or <0.000001

abs = absolute; LLN = lower limit of normal; ULN = upper limit of normal

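### The low neutrophil limit in SAP Appendix Table 2 works out to 0.001 cells/µL, so the planned abnormality displays would in practice flag only a reported zero

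*SAP*

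**What the plan says.** SAP Section 7, Appendix Table 2 sets the hematology criteria for markedly abnormal values. The row for absolute neutrophils is in 10^9/L and reads ">1.5 × ULN or <0.000001". The platelet row, in the same unit, reads "<150 or <200 with a decrease of at least 100". The total white cell row reads ">1.5 × ULN or <LLN", and the eosinophil row has the same criterion. The basophil, lymphocyte and monocyte rows also take the lower limit of normal (LLN) as their low limit.

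SAP 5.8.4 ties these criteria to the reported output: "Potentially clinically significant values can be found in Appendix 1 tables 1-3". It then plans three displays that depend on them:

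- a patient-level table: "Frequency tables of patients with potentially clinically significant laboratory parameter values at any time point will be generated";
- a count of values: "The total number of potentially clinically significant values will also be summarized";
- a listing: "values meeting the potentially clinically significant abnormalities criteria will be presented in data listings".

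The same section plans output that does not use the appendix limits. It summarises extremes and final values ("Baseline value, highest/lowest postbaseline value, and final observation and the corresponding change from Baseline will be summarized for treated patients and untreated patients"), cross-tabulates low, normal and high status against baseline in a shift table where applicable, and lists every laboratory value.

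**The concern.** A low limit of 0.000001 in units of 10^9/L is, for practical purposes, zero. A criterion that only a zero count can meet does no work as a flag for low neutrophils. It is also out of line with every neighbouring row that has a low limit.

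Safety is the primary objective, laboratory abnormalities are a named safety endpoint (Protocol 8.3.1, SAP 3.2.1), and neutrophils are on the protocol's hematology panel (Protocol 11.3.3). Because the row does contain a low criterion, a reader of the finished tables could take an empty low-neutrophil result as evidence that no low counts occurred, when the limit could hardly have detected one. SAP 6.1 also drops the by-visit laboratory summaries planned in the protocol, which leaves the abnormality tables carrying more of the reporting.

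**Working it through.** **Inputs.** From SAP Appendix Table 2: low limit 0.000001, unit 10^9/L. The documents do not give the precision to which the laboratory reports neutrophils, so 1, 2 and 3 decimals are taken as an assumed range. The SAP gives the limit without a derivation, so there is no calculation of the sponsor's to reproduce.

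**Step 1: convert the limit.**

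- Per litre: 0.000001 × 10^9 = 1,000 cells/L.
- Per millilitre: 1,000 ÷ 10^3 = 1 cell/mL.
- Per microlitre: 1,000 ÷ 10^6 = 0.001 cells/µL.

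**Step 2: find what could be flagged.** With d decimals, the smallest non-zero result is 10^-d. It is below 10^-6 only if d is 7 or more. At d = 6 it equals the limit and is not below it.

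| Assumed decimals | Smallest non-zero result (10^9/L) | In cells/µL | Multiple of the limit | Flagged low? |
|---|---|---|---|---|
| 1 | 0.1 | 100 | 0.1 ÷ 0.000001 = 100,000 | No |
| 2 | 0.01 | 10 | 0.01 ÷ 0.000001 = 10,000 | No |
| 3 | 0.001 | 1 | 0.001 ÷ 0.000001 = 1,000 | No |

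Test values of 0.001, 0.01, 0.1, 0.2, 0.5, 1.0 and 1.5 × 10^9/L all went unflagged. Only an exact zero was flagged.

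**Step 3: check the unit against the rest of the table.** The platelet limit of 150 in the same unit is 150 × 10^9 ÷ 10^6 = 150,000/µL, so the unit column is being used on its ordinary scale there. Of the six white-cell rows (total, basophils, eosinophils, lymphocytes, monocytes, neutrophils), five use LLN as the low limit. Neutrophils alone carry a fixed number.

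**Step 4: look for an explanation.** The printed number would equal 1,000 cells/µL if the unit were 10^9/µL (0.000001 × 10^9 = 1,000). That fits a slip by a factor of 10^6 between per-litre and per-microlitre scales, but the documents do not confirm it. No readable text gives another neutrophil limit, and the readable entries in SAP 6.1 do not mention a zero-only rule.

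**The case against.** The strongest contrary case is about weight. The shift table in SAP 5.8.4 is planned in each direction for tests that can be significantly low and significantly high, and the appendix gives neutrophils criteria in both directions. On that reading, low neutrophils would be tabulated by group whatever the appendix limit says. Low counts would also appear in the extremes summary and the full listings. Protocol 11.3.3 has the laboratory flag out-of-range values for investigator review. Low neutrophils are not among the adverse events of special interest (SAP 5.8.2) or the additional events for review (SAP 5.8.3). The protocol's commitment to frequency tables (14.8.2.3) covers selected parameters and does not name neutrophils. Finally, the table was machine-read from a PDF, so the digits could be a reading error.

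Most of this stands as a bound on the harm. Patient-level detection does not depend on the limit, and a low total white count is still flagged by its own LLN rule. Three qualifications apply:

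- The shift table is planned only where applicable and uses low/normal/high status. It does not replace a count against the predefined limit and may disagree with it.
- A low total white count is not a neutrophil finding. Adverse event reports are only a partial backstop, because Protocol 12.2.1 counts test abnormalities as events when they change medical care.
- The neutrophil row is intact and aligned with its neighbours. Checking the source page is sensible, but nothing in the row suggests corruption.

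A programmer might notice the number and replace it. The limit would then be chosen during programming and not in the plan.

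**Conclusion.** The concern holds. As printed, the low neutrophil criterion is 0.001 cells/µL, and three planned displays would show no non-zero low result. This rests on the digits and unit being as printed and on results being reported to six decimals or fewer. The conclusion is the same at any such precision.

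The size is modest: one direction of one parameter, in descriptive safety output. The criterion for high neutrophils still works. The number of patients affected cannot be estimated without the intended limit. It should still be corrected, because it is a wrong threshold feeding displays that support a named safety endpoint, and those displays would be uninformative on low neutrophils.

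**What to change.** The sponsor should check the cell against its source, reconcile the number with its unit, and state the intended low neutrophil limit in 10^9/L. That may be the fixed value originally meant, or LLN as in the five other white-cell rows. The documents do not settle which, and this review does not choose. The patient table, value count and listing in SAP 5.8.4 should then be produced from the corrected limit.

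The cost is one table cell in the SAP and one constant in the program. Some low-neutrophil flags may then appear in the report. If the correction is made after the SAP is final, the clinical study report should note it, as Protocol 14.1 requires for later modifications.
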